9.2.2 Primary Performance Endpoint

Technical Success defined as final residual stenosis $\leq 50\%$ without flow-limiting dissection (\geq Grade D) of the lesion by angiographic core lab. Primary Performance will be assessed on a per-lesion basis.

9.3 Sample Size Determination

Per ISO 14155:2020 (Annex I, Section 1.4), the Mini S Feasibility study is considered to be an exploratory clinical investigation that does not have pre-specified primary hypotheses. For feasibility studies, sample sizes between 12 and 50 have been recommended [21-25]. The sample size for the Mini S Feasibility study (up to n=50) is in keeping with these published recommendations.

	No.: CP 65324	REV. D
	TITLE: Mini S Feasibility Study Protocol	
	CLASS: CLINICAL PROTOCOL	PAGE 38 OF 70

9.4 Populations for Analysis

The primary analysis population will be the Intent-to-Treat (ITT) cohort which includes all enrolled subjects.

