7.7.4 Definition of Enrollment

The definition of enrollment is when the subject signs informed consent, meets all general and angiographic eligibility criteria, a 0.014" guidewire has crossed the target lesion, and the Mini S IVL catheter has been inserted over the guidewire and into the body.

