7.7.5 Catheter Delivery & Crossover (if required)

If the Investigator is able to pass a guidewire but is unable to deliver the Mini S IVL catheter to the proximal edge to the target lesion, an adjunctive tool may be used prior to re-insertion of the Mini S IVL Catheter. Allowable adjunctive tools include guide catheter, guide extension catheter, buddy wire or buddy balloon, and PTA balloon. Atherectomy, cutting/scoring balloons, and specialty crossing devices should not be used. All adjunctive tools used during the procedure should be documented.

If the Mini S IVL Catheter still cannot be delivered to the proximal edge of the target lesion, the user may cross over to the other Mini S catheter configuration (Standard or Flex depending on which configuration was used first). All crossovers should be documented.

If the user is unable to advance any Mini S IVL Catheter to the proximal edge of the target lesion after crossing over to the alternate Mini S configuration, this is considered an **IVL Device Failure**. Treatment should continue per standard of care for the subject.

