9.0 DATA ANALYSIS PLAN

9.1 General Statistical Methods

Descriptive statistics will be provided in this study. Analyses will be conducted at pre-specified time points including 30 days, 6 and 12 months post procedure.

Categorical variables will be summarized by the number of observations available, frequency, and percentage. Unless otherwise noted, missing data will be excluded from the denominator. Clinical outcomes analyzed at 30 days will be evaluated as categorical (binary) data. Exact confidence intervals will be generated for estimates of proportions.

Continuous variables will be summarized by the mean, standard deviation, median, minimum and maximum. Asymptotic confidence intervals will be generated for estimates of means.

9.2 Statistical analyses will be performed using SAS System® Version 9.4 or higher. Primary Endpoints

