9.5 Handling of Dropouts or Missing Data

No imputation of or adjustments for missing data will be performed for the primary analyses. All available data will be presented. For time to event analyses, subjects who do not experience the event in question will be censored at their last known follow-up.

	No.: CP 65324	REV. D
	TITLE: Mini S Feasibility Study Protocol	
	CLASS: CLINICAL PROTOCOL	PAGE 39 OF 70

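### Primary Technical Success is in effect an available-case rate: a target lesion with no readable final core-lab result leaves the denominator, although the primary population is all enrolled subjects

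*Protocol*

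**What the plan says.** Four statements in section 9 of the protocol act together.

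- 9.4: the population for the primary analysis is the "Intent-to-Treat (ITT) cohort which includes all enrolled subjects".
- 9.1, on categorical variables: "Unless otherwise noted, missing data will be excluded from the denominator". The same section calls for exact confidence intervals for proportions.
- 9.5: "No imputation of or adjustments for missing data will be performed for the primary analyses".
- 9.2.2: Technical Success is judged by the angiographic core lab on the final residual stenosis and on the absence of a flow-limiting dissection. "Primary Performance will be assessed on a per-lesion basis". No rule is given for a lesion that the core lab cannot read.

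Three statements in section 7.7 bear on who is in the cohort and what is imaged.

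- 7.7.4: enrolment is complete once consent and eligibility are met, the guidewire has crossed and "the Mini S IVL catheter has been inserted over the guidewire and into the body". This comes before delivery to the lesion, crossing or pulsing.
- 7.7.5: if no Mini S configuration can be delivered to the lesion, this is an IVL Device Failure and "Treatment should continue per standard of care for the subject". Section 7.7.6 says the same for failure to cross.
- 7.7.1 and 7.7.10: a final cine is required for each target lesion, and all angiographic images go to the core lab.

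**The concern.** A reader who sees an all-enrolled population in 9.4 will expect every target lesion of every enrolled subject to be in the primary performance rate. The rules in 9.1 and 9.5 give something else: the rate among lesions with a readable final cine.

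The difference matters if readings are lost for reasons connected with the outcome. Subjects enter the cohort at catheter insertion, so a procedure that is stopped or becomes complicated afterwards stays in it. Such a procedure could plausibly end without a usable final cine. If so, the lesions removed would tend to be the less successful ones, and both the rate and its lower confidence limit would be too high.

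The study has one arm and tests no hypothesis, so the absolute rate and its interval are the performance result. Section 6.2 intends the study to inform the parameters of a pivotal investigation.

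**Working it through.** The protocol states no expected Technical Success rate, missing rate, power or alpha, so there is no figure of its own to reproduce. The check traces the rule and then sizes its effect.

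**Tracing the rule.** Take a target lesion of an enrolled subject with no readable final cine.

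1. By 7.7.4 and 9.4 the subject belongs to the primary population.
2. By 9.2.2 the outcome needs a core-lab reading of the final image, so the lesion's outcome is missing.
3. By 9.1 a missing value leaves the denominator unless an exception is noted; 9.2.2 notes none.
4. By 9.5 nothing is imputed or adjusted for in the primary analyses.

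The lesion therefore counts in neither numerator nor denominator.

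**Inputs.**

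- Target lesions *N*: 50 to 100 at full enrolment, from up to 50 subjects with one or two target lesions each (6.5).
- Unread lesions *m*: 2 or 3, an assumption.
- Observed failures: 0, with one variant of 2, both assumptions.
- Interval: exact (Clopper-Pearson), as 9.1 requires. The 95% level is assumed because 9.1 gives none.

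**Formulas.** With *s* observed successes, the available-case rate is s/(N−m) and the rate with unread lesions counted as failures is s/N. The gap is

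s/(N−m) − s/N = [s/(N−m)] × m/N.

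With no observed failures the gap is simply m/N: 2 points per unread lesion at N = 50 and 1 point at N = 100. For *s* successes among *n* lesions, the exact limits are the 0.025 quantile of Beta(s, n−s+1) and the 0.975 quantile of Beta(s+1, n−s). When s = n, the lower limit reduces to 0.025^(1/n); for example, 0.025^(1/48) = 0.926.

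**Results** (exact 95% intervals in brackets; falls in percentage points).

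| N | Observed failures | m | Available-case rate | Unread = failure | Fall in rate | Fall in lower limit |
|---|---|---|---|---|---|---|
| 50 | 0 | 2 | 48/48 = 100% (92.6–100) | 48/50 = 96.0% (86.3–99.5) | 4.0 | 6.3 |
| 50 | 0 | 3 | 47/47 = 100% (92.5–100) | 47/50 = 94.0% (83.5–98.7) | 6.0 | 9.0 |
| 50 | 2 | 3 | 45/47 = 95.7% (85.5–99.5) | 45/50 = 90.0% (78.2–96.7) | 5.7 | 7.3 |
| 100 | 0 | 2 | 98/98 = 100% (96.3–100) | 98/100 = 98.0% (93.0–99.8) | 2.0 | 3.3 |
| 100 | 0 | 3 | 97/97 = 100% (96.3–100) | 97/100 = 97.0% (91.5–99.4) | 3.0 | 4.8 |

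**Where the available-case rate lies.** The true rate over all *N* lesions lies between s/N and (s+m)/N. With no observed failures the upper bound is 100%, which is the available-case rate itself. In the third row the bounds are 45/50 = 90.0% and 48/50 = 96.0%, against an available-case 95.7%. The rule as written reports a figure at or near the favourable end of what the data allow.

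**The case against.** The case against is substantial, and much of it stands.

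- A reader might infer that 9.4 and 9.1/9.5 contradict each other. They do not, strictly. Section 9.4 says whose data are analysed; 9.1 and 9.5 say how unobserved values within that group are summarised.
- A reader might infer that the intent-to-treat label conceals the loss. It does not. Section 9.1 requires the number of available observations to be shown, so a result of 48/48 beside 50 target lesions would be visible. A required final cine that was not obtained would also be a deviation, and 12.3 classes deviations involving the primary endpoint as major.
- A reader might infer that device failures drop out. They need not. Technical Success is judged on the final result, so a lesion treated by standard of care after a device failure can be imaged, read and scored, possibly as a success. IVL Device Success (5.2) is reported separately and does not depend on a core-lab reading.
- The endpoint is acute and the final cine is mandatory, so few readings may be lost. That the lost ones would be failures is inference; no passage gives a rate or reasons.
- The study is descriptive (6.3, 9.3), so no error rate or decision threshold is affected.

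None of this alters the rule itself. The protocol fixes it rather than leaving it open. The qualifier in 9.1 would let a statistical analysis plan note an exception, but the sentence in 9.5 has no such qualifier. A plan that scored an unread lesion as a failure in the primary analysis would sit uneasily with 9.5. A worst-case sensitivity row would be compatible with the present text, but nothing there requires one.

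**Conclusion.** The point holds in a limited form. As written, primary Technical Success is an available-case rate in a cohort defined as all enrolled subjects, and no rule says how an unread lesion of a stopped or complicated procedure is to be scored. If such lesions occur, the rate is likely to be biased upward; if none occur, the result is unchanged.

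Under the assumptions of 2 or 3 unread lesions, no observed failures and all unread lesions being failures, the lower limit falls by about 6 to 9 points with 50 target lesions and about 3 to 5 points with 100. The larger range should not be quoted alone, because it applies only to one lesion per subject. The intervals also treat lesions as independent. The change is worth making because the absolute rate is the main performance result, but it corrects a possible bias, not a demonstrated one.

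**What to change.** - **9.2.2:** state that the denominator is all target lesions of enrolled subjects. Count as not successful any lesion with no final core-lab reading because the procedure was stopped or complicated. This makes the event part of the outcome definition rather than a missing value.
- **9.2.2, technical losses:** where a cine is lost or unreadable for purely technical reasons, report the available-case rate with the worst-case rate (missing = failure) beside it.
- **Reporting:** give the number of lesions without a final reading, and the reasons.
- **9.1 and 9.5:** note this exception for the primary performance endpoint, so that the three sections agree.

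The cost is a few sentences and one table row. No new assessment is needed, since the final cine is already required. The downside is that the reported rate may be slightly less favourable.

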9.5 Handling of Dropouts or Missing Data

No imputation of or adjustments for missing data will be performed for the primary analyses. All available data will be presented. For time to event analyses, subjects who do not experience the event in question will be censored at their last known follow-up.

	No.: CP 65324	REV. D
	TITLE: Mini S Feasibility Study Protocol	
	CLASS: CLINICAL PROTOCOL	PAGE 39 OF 70

10.0 SAFETY EVENTS

Standard definitions and reporting requirements for reportable adverse events for the study are provided below. All adverse events will be coded using MedDRA.

Note: For any of the Adverse Event Definitions listed below, diagnosis should be reported versus individual symptoms leading to diagnosis.

10.1 Adverse Event Definitions

10.1.1 Adverse Event (AE)

Untoward medical occurrence, unintended disease or injury, or untoward clinical signs (including abnormal laboratory findings) in subjects, users or other persons, whether or not related to the investigational medical device and whether anticipated or unanticipated.

Note: This definition includes events related to the investigational medical device or the comparator.

Note: This definition includes events related to the procedures involved.

Note: For users or other persons, this definition is restricted to events related to the use of investigational medical devices or comparators.

10.1.2 Serious Adverse Event (SAE)

Adverse event that led to any of the following

- a) death,
- b) serious deterioration in the health of the subject, users, or other persons as defined by one or more of the following:
 - 1) a life-threatening illness or injury, or
 - 2) a permanent impairment of a body structure or a body function including chronic diseases, or
 - 3) in-patient or prolonged hospitalization, or
 - 4) medical or surgical intervention to prevent life-threatening illness or injury, or permanent impairment to a body structure or a body function,
- c) fetal distress, fetal death, a congenital abnormality, or birth defect including physical or mental impairment.

Note: Planned hospitalization for a pre-existing condition, or a procedure required by the CIP, without serious deterioration in health, is not considered a serious adverse event.

	No.: CP 65324	REV. D
	TITLE: Mini S Feasibility Study Protocol	
	CLASS: CLINICAL PROTOCOL	

10.1.3 Adverse Device Effect (ADE)

Adverse event related to the use of an investigational device.

Note: This definition includes adverse events resulting from insufficient or inadequate instructions for use, deployment, implantation, installation, or operation, or any malfunction of the investigational medical device.

Note: This definition includes any event resulting from use error or from intentional misuse of the investigational medical device.

Note: This includes “comparator” if the comparator is a medical device.

10.1.4 Serious Adverse Device Effect (SADE)

Adverse device effect that has resulted in any of the consequences characteristic of a serious adverse event.

10.1.5 Unanticipated Serious Adverse Device Effect (USADE)

Serious adverse device effect which by its nature, incidence, severity or outcome has not been identified in the current risk assessment.

Note: Anticipated serious adverse device effect (ASADE) is an effect which by its nature, incidence, severity or outcome has been identified in the risk assessment.

10.2 Adverse Event Device and Procedure Relatedness

Based on clinical judgment, the Investigator must provide a determination of device and procedure relationship for adverse events according to the following categories:

- Causal Relationship (Definite) – The adverse event is clearly related to the study device: the event has a temporal relationship to the study device, follows a known pattern of response, or is otherwise logically related to the study device, and no alternative cause is present.
- Probable – The adverse event is likely related to the study device: the event has a temporal relationship to the study device, follows a known or suspected pattern of response, or is otherwise logically related to the study device, but an alternative cause may be present.
- Possible – The adverse event is unlikely related to the study device: the event does not follow a clear temporal relationship to the study device or does not follow a known pattern of response, or is otherwise possibly to be due to the subject’s clinical state or other modes of therapy.

In some cases, the adverse event may not be adequately assessed because information is insufficient or contradictory and/or the data cannot be verified or supplemented. Maximum effort will be made to define and categorize the event and avoid these situations. If relatedness remains uncertain, then classify the event as “possible”.

.

	No.: CP 65324	REV. D
	TITLE: Mini S Feasibility Study Protocol	
	CLASS: CLINICAL PROTOCOL	PAGE 41 OF 70

- Not Related – The adverse event is clearly not related to the study device: the event has no temporal or other relationship to the administration of the investigational device, follows no known or suspected pattern of response, and an alternative cause is present.

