7.9.1 When and How to Withdraw Subjects

Subjects may be withdrawn with the medical discretion of the physician, or they may voluntarily withdraw their consent at any time without impact to their medical treatment. When a subject is withdrawn, all data obtained prior to the time of withdrawal may be submitted to the Study Sponsor and be included in the study database, unless otherwise requested by the subject in writing.

In the event a subject is lost to follow-up or cannot be contacted for post-treatment assessments, at least three attempts (two phone calls and a certified letter) will be made to locate the study subject, and these efforts will be documented. If the subject cannot be located, the subject's lost to follow-up status will be documented in the EDC and they will be exited from the study.

Should the subject expire, adverse event and study exit/withdrawal forms should be completed. Physician assessment is required to determine if the cause of death was possibly or definitely related to the Mini S Peripheral IVL Catheter. If available, copies of the death certificate and/or an autopsy report should be included in the research records. The Investigator may need to provide written notification to the IRB/EC upon the death of the study subject, dependent on the IRB/EC policies. Associated regulatory bodies may also be required to be notified depending on local jurisdiction and relatedness to the study device and procedures.

	No.: CP 65324	REV. D
	TITLE: Mini S Feasibility Study Protocol	
	CLASS: CLINICAL PROTOCOL	PAGE 35 OF 70

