10.4.2 SAE Reporting Requirements

Any AE meeting any of the criteria for an SAE occurring at any time during the study (enrollment through 12 months) must be reported to the Study Sponsor within 2 business days after the designated study site personnel first learns of the event. The SAE must also be reported to the IRB/EC per the institution's policy for reporting SAEs. SAEs should be reported in the subject's medical records as applicable and on the Adverse Event Case Report Form (AE CRF). Data reported should include date of onset, treatment, resolution, and an assessment of both seriousness and relationship to the study device and procedure. SAEs will be followed until the event has resolved (in the case of permanent impairment, the event will be followed until it stabilizes, and the overall clinical outcome has been ascertained).

It is the responsibility of the Investigator to inform their IRB/EC of serious adverse events as required by their local IRB/EC policies. The Investigator should forward a copy of this report to the Study Sponsor and file in the site regulatory binder.

The Clinical Events Committee (CEC) will review and adjudicate SAEs. See section 13.1 for information on the CEC.

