13.0 STUDY COMMITTEES

13.1 Clinical Events Committee (CEC)

To meet the ethical responsibilities and standards for research subjects, an independent Clinical Events Committee shall serve as forum for adjudication of certain pre-specified clinical event types, including SAEs, as described in the CEC charter.

The CEC will be managed by [REDACTED].

In order to enhance objectivity and reduce the potential for bias, the CEC shall be independent of the Study Sponsor as well as the study investigators.

The CEC is made up of clinicians with pertinent expertise who are not participants in the study and who do not have any other real or potential conflicts of interest. Members have expertise in peripheral endovascular procedures, are experienced in the conduct of controlled clinical trials and have knowledge of bioethics and integrity related to the duties and responsibilities to be performed.

The CEC is charged with the development of specific criteria used for the categorization of adverse events and clinical endpoints in the study. Criteria will be established for selected complications and clinical events. Events to be adjudicated include death, MAEs, revascularizations, and amputations. The CEC will also adjudicate relationship to the study device and study procedure according to the following classifications: definitely related, probably related, possibly related, unlikely related and not related.

At the onset of the study, the CEC will establish explicit rules outlining the minimum amount of data required and the algorithm followed in order to classify an event. The methodology for performing these responsibilities shall be developed and outlined in the CEC Charter. Operational provisions shall be established to minimize potential bias (i.e., CEC members shall be blinded to the clinical site to the extent possible during adverse event review and adjudication). The methodology for performing these responsibilities shall be developed and outlined in the CEC Charter. In addition, the CEC Charter will include the number of members, responsibilities, CEC meeting procedures, and meeting frequency.

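### Section 10.2 defines the relatedness level *Possible* as unlikely to be related, while the CEC grades the same SAEs with possibly and unlikely as separate levels

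*Protocol*

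**What the plan says.** Section 10.2 asks the investigator to grade each adverse event for its relationship to both device and procedure, on four levels: Definite, Probable, Possible and Not Related. The third level reads "Possible – The adverse event is unlikely related to the study device". The fourth reads "Not Related – The adverse event is clearly not related to the study device". For events that cannot be assessed adequately the section gives a default, "If relatedness remains uncertain, then classify the event as" possible. All four definitions speak of the study device only.

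Section 10.4.2 requires the site to assess the relationship of each SAE to device and procedure, and adds: "The Clinical Events Committee (CEC) will review and adjudicate SAEs". Section 13.1 lists what goes to the committee ("Events to be adjudicated include death, MAEs, revascularizations, and amputations") and names SAEs among the event types for adjudication. It has the committee grade relationship to device and procedure as "definitely related, probably related, possibly related, unlikely related and not related". The protocol does not define these five levels. It leaves criteria and method to the CEC charter.

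**The concern.** A label and its definition should not contradict each other on a form that investigators complete for every adverse event. Here the word *Possible* points one way and its definition the other. An investigator who reads the label and one who reads the definition may place the same event differently. One who follows the definition records a judgement of unlikely under a name that most readers of a table will take to mean something stronger.

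The CEC then grades the same SAEs on a scale that keeps the two notions apart. A comparison of investigator and CEC relatedness would show disagreement where there is none.

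What is at stake is the description of device-related events. Section 10.1.3 makes relatedness the defining feature of an ADE, Section 10.1.4 builds SADE on it, Section 10.4.4 has the sponsor evaluate ADEs for SADE status, and Section 12.0 makes the sponsor responsible for classifying adverse events. Section 6.3 describes this as the device's first evaluation in human subjects, so these descriptive counts will be read closely.

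**Working it through.** No arithmetic applies beyond counting levels. The protocol states no figure to reproduce, so the check sets the two scales side by side.

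| Order | Investigator (Section 10.2) | Sense of the definition | CEC (Section 13.1; no definitions given) |
|---|---|---|---|
| 1 | Definite | clearly related | definitely |
| 2 | Probable | likely related | probably |
| 3 | Possible | unlikely related | possibly |
| 4 | Not Related | clearly not related | unlikely |
| 5 | (none) | | not related |

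1. **Level count.** The investigator has 4 levels and the CEC has 5, a difference of 5 − 4 = 1. The level without a counterpart by name on the investigator's side is unlikely.

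2. **An event the investigator thinks unlikely to be related.** Definite and Probable do not fit. Not Related does not fit, because it requires the event to be clearly unrelated, with an alternative cause present. Possible fits, because its definition uses that very term. The recorded label is *Possible*.

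3. **The same event, if the CEC also thinks it unlikely to be related.** Section 13.1 offers a level with that name. The recorded label is *unlikely related*.

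4. **Do both graders see the same event?** Yes, for SAEs. Section 10.4.2 requires the site's relationship assessment and also sends SAEs to the CEC. Non-serious events outside the CEC's list get the investigator's label only. For them the contradiction inside Section 10.2 remains, but there is no second label to conflict with it.

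5. **Where does relatedness act?** It acts in ADE, SADE and USADE classification (Sections 10.1.3 to 10.1.5) and in tables of related events. It does not enter the primary safety endpoint: Section 9.2.1 counts CEC-adjudicated MAEs whatever their cause. It does not change how fast the site must report. In Table 3 (Section 10.4.6), SAE and SADE share one row at 2 business days, USADE has the same 2-business-day limit, and non-serious AE and ADE share one row. Section 13.2 has the DSM evaluate all adverse events, and its immediate-notification triggers do not refer to the Section 10.2 levels.

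6. **Direction.** An unlikely-related event carries a label that sounds more related than the judgement behind it. The error is an over-call at site level, and no event drops out of view.

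7. **Device and procedure.** The lead-in of Section 10.2 asks for both relationships, but none of the four definitions mentions the procedure. An investigator grading procedure relatedness has no matching text.

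**The case against.** The strongest reply is that almost nothing in the protocol depends on this scale. Endpoints, site deadlines and DSM review do not use it, and the error is on the cautious side. That stands, and it is why the point is minor. Two graders holding independent views is also no fault in itself, since that is the purpose of an independent CEC. The fault is narrower: one definition contradicts its label, and the same judgement gets two names.

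Several stronger readings are tempting but not supported:

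- **That one investigator level covers two CEC levels.** Section 13.1 names its levels without defining them. An event with a temporal link and a possible alternative cause fits the Section 10.2 text for Probable, so a CEC grade of possibly related need not correspond to *Possible*. Only the mismatch on unlikely can be shown.
- **That the default for uncertain events is wrong.** It is an explicit, conservative rule that applies only after every effort to categorise the event.
- **That Section 7.9.1 sets a threshold for deaths.** It says "Physician assessment is required to determine if the cause of death was possibly or definitely related to the Mini S Peripheral IVL Catheter" and also "Associated regulatory bodies may also be required to be notified depending on local jurisdiction and relatedness to the study device and procedures". The first sentence omits probably, but it is an instruction for documenting a death and not a grading scale. The second ties notification to local rules and relatedness in general. Neither states a cut-off.
- **That the protocol is defective because it does not say which levels count as related, or whose grade is tabulated.** Such rules may sit in the statistical analysis plan or the CEC charter, neither of which is at hand.

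The charter could define or map the CEC's levels. It could not correct the definition that investigators apply at data entry.

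**Conclusion.** The contradiction stands in the current text of Sections 10.2 and 13.1, and no other section repairs it. It does not rest on the revision history. Followed as written, Section 10.2 records an event judged unlikely to be related as *Possible*, and the CEC's label for the same judgement on the same SAE is different.

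The size is structural: 4 levels against 5, with one judgement carrying two names. How many events are affected cannot be derived from the protocol, and no rate is claimed. The consequence is limited to relatedness labels, descriptive device-related counts and ADE/SADE classification. How far those counts shift depends on which levels are treated as related, which the protocol does not state. The conclusion assumes only that investigators follow the written definition and that the CEC uses its level names in their ordinary sense. Severity: minor.

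**What to change.** - Reword *Possible* in Section 10.2 so that it does not mean unlikely, for example as a relationship that cannot be excluded.
- Align Sections 10.2 and 13.1. Either use one set of level names and definitions for both graders, or keep both scales and state explicitly which investigator level corresponds to the CEC's *unlikely related*.
- Word the Section 10.2 definitions for the procedure as well as the device, as the section's own lead-in requires.

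The default that puts uncertain events under *Possible* can stay.

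The cost is small: short edits to the protocol, the CRF and the CEC charter. The limitation is that events already graded *Possible* stay pooled unless they are re-graded.
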